Verbal consent will be documented on the recruitment form and in REDCap and a copy of the IRB-approved consent form will be mailed to participants for their records. All study data outside of REDCap will be stored in a locked cabinet at the Center for Health Enhancement Systems Studies at the UW.

Baseline interviews will be conducted with the drinker and partner individually over the phone.

Once dyads complete the pretest, the UW team will send phones and train drinkers and partners on the appropriate technology. Dyads will be informed that they will stay in the study if they do not miss two surveys in a row. If the drinker or partner declines, the dyad will be excluded. We will document reasons for refusals and monitor whether refusal rates differ by sex, race/ethnicity, and age. We will also note race/ethnicity and whether partners are of the opposite or same sex.

Recruitment sources. Many couples participating in our R34 PartnerCHESS study were recruited not from AUD/SUD treatment agencies but from advertisements in Craigslist and an email blast sent to faculty and staff at the University of Wisconsin–Madison; this indicates there is a large segment of people not in treatment who want and need help. Ultimately, our approach will be to recruit and serve dyads from addiction treatment agencies, hospitals that identify individuals with AUD, and the wider world where individuals may not have access to treatment or avoid it because of stigma. This will be a nationwide recruitment using platforms such as email marketing, targeted over-the-air advertising delivered through streaming platforms (e.g. Roku, Amazon Fire TV), local broadcast television, Craigslist, Facebook, and an email blast sent to faculty and staff at the University of Wisconsin. to increase awareness of opportunities to get help. We will also purchase advertising in newspapers that traditionally reach African American populations.

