Data collection. Surveys will be conducted with both members of the dyad in all three study arms every 4 months (baseline, 4, 8, and 12 months). Each participant receives \$25 per completed survey. Payments will be processed in 2 ways. If the participant prefers to receive the payment in the mail, we will send cash to the participant within 5 business days of their survey being completed. If the participant prefers to receive payment through a mobile app, we will send them payment through Venmo or Paypal.

UW staff blind to the hypotheses will conduct the surveys. To ensure fidelity and data quality, we will record interviews, and [name] will review a subset and provide feedback. All uses of the apps are automatically logged to create measures of use of different services. Survey data will be double-entered into ICTR REDCap and compared to reduce the chance of data-entry errors. Both survey and app data are stored on a UW Division of Information Technology HIPAA-secure server using the Campus Computing Infrastructure. The timing of interviews will be based on enrollment date.

Once the trial begins, we will analyze app use data every 2 weeks to note trends in services used most and differences in use patterns between drinkers and partners. One tool for drinkers in ACHESS-C and FamCHESS-C will be a weekly survey adapted from the Brief Alcohol Monitor (BAM),81 with four COVID-related protective behavior questions added. Our adaptation of the BAM asks about 5 factors that put patients at risk of relapse and 5 factors that protect. Responses help CHESS systems tailor services to individual patients and partners. We will also add questions to the every-4-months interviews. Some app-based questions will change over time as we explore specific issues. For instance, if a service is not used for a month, we will add a question about why. If certain services are used a great deal, we will ask how and why it's useful, to understand if additional related resources are needed.

Keeping patients and partners engaged. Other CHESS studies have increased engagement in 4 ways. We will use all: 1) Monitor and respond to changes in the amount of app use. 2) Examine discussion posts using tools we developed that are based on Linguistic Inquiry and Word Count74 and machine learning82-84 to

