automatically predict relapse and intervene (e.g. an alert sent to a counselor). 3) Use ecological momentary assessments and weekly check-in data to identify and act on disconcerting trends (e.g. call to ask how the person is doing; refer users to relevant app services, games, and customized tips to address concerns, e.g. sleep). 4) Like other content-based or social media apps (e.g. NYT.com, FaceBook), relevant new information, resources, and user-generated content across the range of app topics, including alcohol use, couple skills, and COVID-19, is continuously added so that people keep coming back.

If drinkers stop using the app. We will be automatically notified of drinker non-use lasting 2 weeks. The project director will then make contact to resolve problems and encourage use. Those not using their app will still be included in the post-test interviews to understand reasons for stopping.

Dissolution of the relationship. If a family partner and drinker separate, we will encourage both to continue the study. At either's request, we will disengage portions of FamCHESS-C connecting them to each other. If one wishes to quit, we will honor their choice but encourage them to continue answering surveys.

Qualitative interviews. We will conduct qualitative interviews with a subset of participants who were randomized into the FamCHESS arm. Interview questions were developed by the study investigators to fill in the gaps where quantitative data alone may fall short. For example, how they decided to join the study, did they use the app together, did the app spark specific behavior change techniques. We will contact participants by phone or email to see if they are interested in taking part in a 45-minute qualitative phone interview. We will try to reach participants a maximum of three times. This is the script for leaving a voicemail:

"Hi. This is <name of study staff> from the UW Partner Study. I'm checking to see if you'd be interested in doing a phone interview with us so we could learn about your experience using the PartnerCHESS app. It will take about 45 minutes, and we would compensate you \$20 for taking part. Call or text if you're interested in finding out more. I'll also send you an email message to see if you're interested. Thanks!"

This is the script for leaving an email message:

Subject Line: UW Interview Opportunity

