Summary of ACHESS-C and FamCHESS-C arms. In ACHESS-C, both the drinker and the partner will receive a smartphone, but only the drinker will receive the ACHESS-C app. The partner will receive a smartphone with contact information for standard AUD, SUD, and crisis support. In the FamCHESS-C arm, drinker and partner will both receive a smartphone with the FamCHESS-C app, which contains ACHESS-C services plus ABCT/ PartnerCHESS services. As described below, both the ACHESS-C and FamCHESS-C apps will contain services designed to address relapse factors of lifestyle imbalance, desire for indulgence, urges and cravings, high-risk situations, low selfefficacy, lack of coping responses, previous lapses, and abstinence violations.

ACHESS-C services. ACHESS-C offers the following, which are also available in FamCHESS-C:

COVID content. COVID-relevant materials are incorporated into multiple services: instant library (COVID information), personal stories (how others have prevented or dealt with COVID), risk assessments (evaluate-your-risk simulation), crisis assessments (what to do if infected), warning signs (possible infection or vaccine side effects), healthy/safe/fun things to do together, surveys (adherence to preventive behaviors), and reminders (COVID prevention and vaccine opportunities).

Instant library. Frequently asked questions and brief information on addiction and couples-related issues (e.g. taking care of yourself, financial matters, substance abuse, crisis intervention, referral, medications).

Discussion groups. Forums connect patients or partners with others. Posts are analyzed to predict relapse.

Optional Video Meetings: Regularly scheduled group meetups facilitated by research staff via zoom. Attending video meetings is completely optional and study participants can choose to have their camera on or off, and no one is required to speak. To foster open and honest dialogue, each meeting will be held for each specific group in the study. So, participants in different groups will not be able to attend another group's meeting.

Personal stories. Audio/video of patients and family partners talking about experiences dealing with addiction. The audio/video is not of active study participants, but volunteers willing to share their experiences.

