Hard copy data, such as surveys, will not contain identifying information. They will be stored in a locked file cabinet in the study coordinators private office. Electronic data, such as A-CHESS-C or FamCHESS-C use data, will be stored on a secure, HIPAA-compliant UW-Madison DoIT server. Access to this data will be limited by granting individuals access via their UW user log-in. Paper study data, such as surveys and contact information, will be entered into a REDCap system managed by ICTR.

Any data stored on a participant's device are stored in an encrypted file and only accessible by that participant, i.e. participants won't have any other participant data on their phone. These data are only collected after the participant has signed into their account and are removed when the participant signs out of the A-CHESS-C or FamCHESS-C application. Any data transferred to and from CHESS servers are done through an encrypted connection.

A list of subject code numbers will be maintained by the UW study coordinator and stored in an electronic spreadsheet. This data will be kept in a secure, limited access,

password-protected file on CHESS servers which are located in the department of Systems and Industrial Engineering in the Mechanical Engineering building on the 4th floor.

The study coordinator will be the only person with access to both the coded study data and the subject identifiers.

When all study activities are complete identifiable information will be destroyed. Deidentified study data will be stored on the secure CHESS servers for potential future unspecified research for which new IRB submissions will be initiated.

Potential Risks:

Regarding risk of misinterpretation of information: Information and resources on the A-CHESS-C/FamCHESS-C apps will be screened by experts from our project team as well as from our Steering Committee for accuracy. Additionally, messages exchanged within the apps will be monitored to make sure the information is accurate and that study participants are using the system for its intended purpose. Inaccurate or harmful statements will be addressed by the CHESS moderator.

Possible breach of confidentiality: All subjects will be assigned a blind code number that will be kept in a locked file in the CHESS office. Data collected from clinic records and smartphone use files will have the name removed and the code number attached by the study coordinator.

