If there is evidence of abuse or of a smartphone user being engaged in criminal activity (e.g., a discussion group being used to sell an illegal drug), we may need to inform an

appropriate authority. Hence our consent form will include the following statement: "I understand that subject anonymity and data confidentiality cannot be maintained if A-CHESS-C or FamCHESS-C finds evidence of abuse, suicidality, or criminal activity."

If participants are incarcerated, no research activities would occur during the time of incarceration. Participants can contact the UW study coordinator if they are released during the original study period and would like to continue on study.

The researchers may also take participants out of the study, even if they want to continue, if they use the phone in an inappropriate manner (i.e. messages including nudity, threats, racism, bigotry), research staff will delete the inappropriate messages and follow up with the participant. If the behavior continues, research staff may decide to withdraw the participant from the study without their consent for their best interest as well as others on the study

If participants experience any crises during the study period, they will be instructed to contact their clinician if currently in treatment. If participants have crises after hours, they will be instructed to call 911 for imminent risk or go to a local emergency room crisis center. All participants will be provided with a listing of crisis hotline numbers and community resources that participants may access 24/7, such as the National Drug Abuse [contact]), the National Domestic Violence [contact]), or a Crisis Hotline for any crisis [contact]).

Lost or Stolen Smartphone: Participants will be informed that if the phone is in the hands of another person there is the potential that someone might see the information they stored on the phone (personal contacts, text messages). Participants are advised to make their phone password protected to reduce the risk of someone being able to see their information if the phone is lost or stolen.

Phone service for the study phone is terminated at the end of the 8-month intervention period. Participants may feel some loss when they no longer have that service. The study coordinator will explain this prior to informed consent and will inform the participants well in advance of the service ending so they have time to get their own service if they wish.

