Intention-to-Treat and Subject Noncompliance. Standard intention-to-treat (ITT) estimates the average treatment effect by comparing outcomes based on assignment of the treatment, but ignoring use of the treatment. Because ITT effect estimates do not represent treatment efficacy under noncompliance (e.g. a drinker is randomized to FamCHESS-C but does not use the system), we will also estimate noncompliance by estimating treatment effects only for compliers, using As-treated, Per-Protocol¹¹⁰ and CACE.¹¹¹

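### The two-missed-surveys rule and study withdrawal for app conduct end follow-up that could continue; the loss is small, falls mainly at month 12, and is cheap to avoid

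*Combined protocol and SAP*

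**What the plan says.** Section 4.0 (Patient Recruitment and Consent) sets a condition for staying in: "Dyads will be informed that they will stay in the study if they do not miss two surveys in a row". It does not say whether a miss by one member counts, or whether staff stop attempting surveys.

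Section 5.0 (Data collection) gives the schedule: "Surveys will be conducted with both members of the dyad in all three study arms every 4 months", that is, at baseline and months 4, 8 and 12. Section 5.0 (Potential Risks) adds a conduct rule. Its trigger is "if they use the phone in an inappropriate manner (i.e. messages including nudity, threats, racism, bigotry". Staff first delete the messages and follow up. If the behaviour continues, "research staff may decide to withdraw the participant from the study without their consent". Nothing is said about outcome surveys afterwards.

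Elsewhere the plan aims to keep people in follow-up. On drinkers who stop using the app, Section 5.0 says: "Those not using their app will still be included in the post-test interviews". Under Dissolution of the relationship, a person who wants to quit is encouraged to go on answering surveys. Section 8.0 describes the main comparison in these terms: "Standard intention-to-treat (ITT) estimates the average treatment effect by comparing outcomes based on assignment of the treatment". It also plans a mixed model that tolerates incomplete data, with pattern-mixture and imputation sensitivity analyses.

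**The concern.** Missing two surveys in a row is unlikely to be unrelated to outcome: relapse, separation and fatigue with the app are all plausible reasons. A rule that then closes follow-up stops the trial from learning how these dyads fared, even when they would have answered.

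The pattern of absent at months 4 and 8 but seen at month 12 is the one that would inform a pattern-mixture analysis about early non-responders, and the rule removes it. A dyad with baseline data only tells the mixed model almost nothing about the arm-by-time effect. Month 12 is a planned time point for both primary outcomes (Table 2).

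The conduct rule raises a second issue. It removes the person from the study rather than from the forum, and the opportunity to trigger it depends on having an app, so missing outcomes could arise unequally across arms.

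**Working it through.** **The plan's own figures.** Section 8.0 (Power) takes 198 dyads to 180 at 10% attrition and 159 at 21%. Direct arithmetic gives 198 × 0.90 = 178.2 and 198 × 0.79 = 156.4, each within 3% of the stated figure. These are 8-month numbers.

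**When the two-miss rule can act.** Baseline precedes randomisation, so the post-baseline surveys are months 4, 8 and 12. Two misses in a row are complete at month 8 at the earliest. Missing 8 and 12 leaves nothing further to lose. Only the month-12 survey of a dyad that missed both 4 and 8 is at risk, so the rule removes no dyad from the 8-month analysis.

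**How many dyads.** Let m be the chance of missing a survey and r the correlation between consecutive misses. Both are assumptions. For m I use 10-21%, which the plan gives as attrition by 8-9 months in earlier studies, not as a per-survey rate. The plan's expected 85% interview completion (m = 0.15) lies inside that range. I also assume that response at month 12 depends only on response at month 8.

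- Trigger the rule: 198 × [m² + r·m·(1 − m)]
- Would have answered month 12: (1 − m)(1 − r)
- Surveys lost to the rule: the product of the two, counted per dyad

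| m | r | Trigger | Would answer at 12 | Lost to the rule |
|---|---|---|---|---|
| 0.10 | 0 | 2.0 | 0.90 | 1.8 |
| 0.10 | 0.5 | 10.9 | 0.45 | 4.9 |
| 0.10 | 0.8 | 16.2 | 0.18 | 2.9 |
| 0.15 | 0.5 | 17.1 | 0.425 | 7.3 |
| 0.15 | 0.8 | 24.7 | 0.17 | 4.2 |
| 0.21 | 0 | 8.7 | 0.79 | 6.9 |
| 0.21 | 0.5 | 25.2 | 0.395 | 9.9 |
| 0.21 | 0.8 | 35.0 | 0.158 | 5.5 |

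For r of 0.5-0.8 the loss is 2.9 to 9.9 dyads, or 1.5% to 5.0% of 198. For scale, 15% missing at month 12 would be 0.15 × 198 = 29.7 dyads. At m = 0.15 the rule adds 4.2 to 7.3 to that, about a seventh to a quarter more.

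**If either member's misses count.** Take members as independent, each with a 15% miss rate and a 50% chance of missing again. Then 198 × [1 − (1 − 0.075)²] = 28.6 dyads trigger the rule. In about half of them (14.3) the member who missed would have answered at month 12. The other member's survey would be lost as well, however willing that person was.

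**Conduct rule.** Each arm has 66 dyads. Control has no app. In ACHESS-C "only the drinker will receive the ACHESS-C app", which gives 66 users. In FamCHESS-C both members have the app, which gives 132. Monitoring is described for the apps: "messages exchanged within the apps will be monitored to make sure the information is accurate". The plan gives no withdrawal rate. At an assumed 1-5% of app users, withdrawals would be 0 in control, 0.7-3.3 people in ACHESS-C and 1.3-6.6 in FamCHESS-C. If those withdrawn were 0.5-1 SD worse than the rest of their arm (also assumed), the arm mean would shift by 0.01 × 0.5 = 0.005 SD to 0.05 × 1 = 0.05 SD. The plan is powered on d = 0.40.

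**The case against.** The strongest reply is that Section 4.0 records only what dyads are told. It sets out no removal procedure and does not say that staff stop calling. That is fair: exit is the implied converse. But it is given as the condition for staying, and no other section says surveys continue after two misses.

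A reader might infer that all 11-35 triggering dyads lose a month-12 value to the rule. They do not. The same correlation that raises the number of triggers makes those dyads likely to miss month 12 anyway.

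A reader might also infer a breach of intention-to-treat. The documents do not support that. Analysis by assignment remains possible, no section discards collected data, the mixed model uses what is observed, and missing-data sensitivity analyses are planned. These do not recover an outcome that was never sought, so what remains is an avoidable follow-up gap.

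On arm dependence, the two-miss rule is worded identically for all arms. The conduct rule speaks of the phone, and every arm has phones. That it bears mainly on app users is an inference from its examples, which are messages, and from where monitoring is described. It also needs repeated behaviour and a staff decision.

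Finally, the provision to keep interviewing people who stop using the app concerns app use, not survey response. The sections pull in different directions but do not flatly contradict each other.

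**Conclusion.** The point holds as a modest, avoidable loss of outcome data. Followed as written, both rules end collection of obtainable outcomes and neither provides for further surveys, which sits badly with the plan's own effort to keep non-users and people who quit in follow-up.

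The cost of the two-miss rule is confined to month 12: about 3-10 surveys under the assumed miss rates and correlations, about 2-7 if misses are independent, and more if either member's misses count. The 8-month sample of 180 or 159 stands. The conduct rule can act at any time and could produce arm-dependent missing data, but on the assumed rates the shift is at most about 0.05 SD. Nothing here shows that the trial's main comparison is invalid. The case for change is that the lost values come from the dyads about which least is known, cannot be recovered later, and cost very little to collect.

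**What to change.** In Section 4.0, replace the two-miss sentence with a statement that every randomised dyad is offered each remaining survey, member by member and including month 12, whatever was missed before. The exceptions are a member's own withdrawal of consent and the provision in Section 5.0 that bars research activities during incarceration.

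In Section 5.0, state that removal for conduct ends app or forum access, that outcome surveys are still offered unless staff document a safety reason not to, and that data already collected are kept and analysed by assigned arm.

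The cost is protocol and consent wording, a few more survey attempts, and the $25 payments. For 2.9 to 9.9 dyads with two members each, the payments come to about $145 to $495 in total (2.9 × 2 × $25 and 9.9 × 2 × $25).

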5.0 TREATMENT PLAN

We will provide an Android smartphone to anyone who does not have one, and we will provide a data plan for 8 months to both partners in all three study arms. If participants already have a smartphone, we will help them download the relevant app onto their phone and pay \$50 per month toward internet service. The apps are compatible with both Android and iOS phones. After 8 months, study participants are no longer part of the active intervention and they will no longer be required to use the app. We will conduct a follow-up survey at 12 months to assess results after the active intervention.

Set-up and training. All enrollment, training and baseline data collection will occur over the phone. Participants will have the option to complete 4, 8 and 12 month surveys over the phone, by completing a paper survey and mailing it back to us, or completing the survey using a secure UW-Madison Qualtrics online survey. Participants who wish to complete a paper survey and mail it back will be provided a self-addressed stamped envelope. After completing consents, baseline interviews, and randomization, UW staff will provide relevant training. Drinkers and family partners in the smartphone control condition and family partners in the ACHESS-C study arm will be given standardized suggestions to use the phone to connect to resources to help with the stresses of

COVID and alcohol use, and will be shown the pre-programmed numbers for support (e.g. AA, Al-Anon) and crisis hot lines. Drinkers in the ACHESS-C study arm will be helped to download the app onto the phone, instructed in the services on the app, and taught to personalize the app, including entering high-risk locations and creating a location alert (e.g. a voice-recording from a partner or other key person expressing love and concern about the drinker being in a high-risk location). The same procedures occur in the Fam-CHESS-C study arm, but in addition, staff will help the drinker and partner enter what motivates them to be healthy and what triggers alcohol or other substance use. Dyads will enter at least one recovery-supporting activity and one social activity or fun thing they will do together. Training sessions will be recorded and reviewed for fidelity. Both the ACHESS-C and FamCHESS-C apps will provide ongoing prompts to use different parts of the app, and there are refresher training videos on the phones, reminding participants how to use the functions they were shown.

Data collection. Surveys will be conducted with both members of the dyad in all three study arms every 4 months (baseline, 4, 8, and 12 months). Each participant receives \$25 per completed survey. Payments will be processed in 2 ways. If the participant prefers to receive the payment in the mail, we will send cash to the participant within 5 business days of their survey being completed. If the participant prefers to receive payment through a mobile app, we will send them payment through Venmo or Paypal.

UW staff blind to the hypotheses will conduct the surveys. To ensure fidelity and data quality, we will record interviews, and [name] will review a subset and provide feedback. All uses of the apps are automatically logged to create measures of use of different services. Survey data will be double-entered into ICTR REDCap and compared to reduce the chance of data-entry errors. Both survey and app data are stored on a UW Division of Information Technology HIPAA-secure server using the Campus Computing Infrastructure. The timing of interviews will be based on enrollment date.

Once the trial begins, we will analyze app use data every 2 weeks to note trends in services used most and differences in use patterns between drinkers and partners. One tool for drinkers in ACHESS-C and FamCHESS-C will be a weekly survey adapted from the Brief Alcohol Monitor (BAM),81 with four COVID-related protective behavior questions added. Our adaptation of the BAM asks about 5 factors that put patients at risk of relapse and 5 factors that protect. Responses help CHESS systems tailor services to individual patients and partners. We will also add questions to the every-4-months interviews. Some app-based questions will change over time as we explore specific issues. For instance, if a service is not used for a month, we will add a question about why. If certain services are used a great deal, we will ask how and why it's useful, to understand if additional related resources are needed.

Keeping patients and partners engaged. Other CHESS studies have increased engagement in 4 ways. We will use all: 1) Monitor and respond to changes in the amount of app use. 2) Examine discussion posts using tools we developed that are based on Linguistic Inquiry and Word Count74 and machine learning82-84 to

automatically predict relapse and intervene (e.g. an alert sent to a counselor). 3) Use ecological momentary assessments and weekly check-in data to identify and act on disconcerting trends (e.g. call to ask how the person is doing; refer users to relevant app services, games, and customized tips to address concerns, e.g. sleep). 4) Like other content-based or social media apps (e.g. NYT.com, FaceBook), relevant new information, resources, and user-generated content across the range of app topics, including alcohol use, couple skills, and COVID-19, is continuously added so that people keep coming back.

If drinkers stop using the app. We will be automatically notified of drinker non-use lasting 2 weeks. The project director will then make contact to resolve problems and encourage use. Those not using their app will still be included in the post-test interviews to understand reasons for stopping.

Dissolution of the relationship. If a family partner and drinker separate, we will encourage both to continue the study. At either's request, we will disengage portions of FamCHESS-C connecting them to each other. If one wishes to quit, we will honor their choice but encourage them to continue answering surveys.

Qualitative interviews. We will conduct qualitative interviews with a subset of participants who were randomized into the FamCHESS arm. Interview questions were developed by the study investigators to fill in the gaps where quantitative data alone may fall short. For example, how they decided to join the study, did they use the app together, did the app spark specific behavior change techniques. We will contact participants by phone or email to see if they are interested in taking part in a 45-minute qualitative phone interview. We will try to reach participants a maximum of three times. This is the script for leaving a voicemail:

"Hi. This is <name of study staff> from the UW Partner Study. I'm checking to see if you'd be interested in doing a phone interview with us so we could learn about your experience using the PartnerCHESS app. It will take about 45 minutes, and we would compensate you \$20 for taking part. Call or text if you're interested in finding out more. I'll also send you an email message to see if you're interested. Thanks!"

This is the script for leaving an email message:

Subject Line: UW Interview Opportunity

"Hi. This is <name of study staff> from the UW Partner Study. I'm checking to see if you'd be interested in doing a phone interview with us so we could learn about your experience using the PartnerCHESS app. It will take about 45 minutes, and we would compensate you \$20 for taking part. If you're interested, email us back or you can call me at <study staff work phone number>."

We will explain that the interview is voluntary, and they can refuse if not interested. Participants will be paid \$20 for completing the interview. To cover a wide range of

experiences with the app, we will look at app use data to find a pool of potential interviewees. Our goal is to interview participants across the spectrum of app use, from very little to very much. Recruitment will continue until thematic saturation has been reached. We define thematic saturation as the point at which additional data lead to no new themes, when the researcher is empirically confident having repeatedly seen similar instances of data, and themes (or patterns in the data) are well-developed with diminishing returns from further data collection. If a participant agrees to the interview but does not want to be audio recorded, we will continue the interview, taking handwritten notes.

Audio recordings will be saved to HIPAA compliant servers managed by UW-Madison's College of Engineering Computer Aided Engineering with restricted access to CHESS study staff. Study staff will create de-identified transcripts for review by researchers. 7 years after study completion, all audio recordings will be destroyed.

Descriptions of the 3 Study Arms.

Summary of smartphone control arm. Both the drinker and family partner will receive a smartphone with pre-programmed contact information for Alcoholics Anonymous (AA), Narcotics Anonymous (NA), Al-Anon, Adult Children of Alcoholics (ACOA), and crisis hot lines.

Summary of ACHESS-C and FamCHESS-C arms. In ACHESS-C, both the drinker and the partner will receive a smartphone, but only the drinker will receive the ACHESS-C app. The partner will receive a smartphone with contact information for standard AUD, SUD, and crisis support. In the FamCHESS-C arm, drinker and partner will both receive a smartphone with the FamCHESS-C app, which contains ACHESS-C services plus ABCT/ PartnerCHESS services. As described below, both the ACHESS-C and FamCHESS-C apps will contain services designed to address relapse factors of lifestyle imbalance, desire for indulgence, urges and cravings, high-risk situations, low selfefficacy, lack of coping responses, previous lapses, and abstinence violations.

ACHESS-C services. ACHESS-C offers the following, which are also available in FamCHESS-C:

COVID content. COVID-relevant materials are incorporated into multiple services: instant library (COVID information), personal stories (how others have prevented or dealt with COVID), risk assessments (evaluate-your-risk simulation), crisis assessments (what to do if infected), warning signs (possible infection or vaccine side effects), healthy/safe/fun things to do together, surveys (adherence to preventive behaviors), and reminders (COVID prevention and vaccine opportunities).

Instant library. Frequently asked questions and brief information on addiction and couples-related issues (e.g. taking care of yourself, financial matters, substance abuse, crisis intervention, referral, medications).

Discussion groups. Forums connect patients or partners with others. Posts are analyzed to predict relapse.

Optional Video Meetings: Regularly scheduled group meetups facilitated by research staff via zoom. Attending video meetings is completely optional and study participants can choose to have their camera on or off, and no one is required to speak. To foster open and honest dialogue, each meeting will be held for each specific group in the study. So, participants in different groups will not be able to attend another group's meeting.

Personal stories. Audio/video of patients and family partners talking about experiences dealing with addiction. The audio/video is not of active study participants, but volunteers willing to share their experiences.

Location monitor. Geo-fencing of areas identified by participants as triggers (e.g. a bar that was frequented) prompts a warning. If the drinker stays in the area, a recorded message encourages him or her to leave. If the drinker does not leave, a supporter is notified. (Our advisors felt that family partners in the FamCHESS-C arm should not monitor drinker location.)

Surveys/ecological momentary assessments. Questions assess immediate needs and trends over time. Partners are asked about their own status and their perspectives on the drinker's status. Advice or referrals to other ACHESS-C or FamCHESS-C services arise from responses to questions as well as from the predictive analytics that examine relapse risk using data, e.g. from discussion groups and surveys.⁷³

Guided relaxation. Audio/video to guide mindfulness, relaxation, games, and other help for cravings.

Meeting locator. Drinkers (and family partners) can use GPS to find AA and Al-Anon meetings.

Healthy activities. Database of ideas (e.g. taking a walk) and local recovery-friendly activities.

*Crisis button.* Relaxation exercises, optional calls to supporters, games for distraction, and other resources.

Skills reminders. Tips and reminders of CBT-based skills (e.g. effective communication, refusal skills).

Predictive analytics. Real-time linguistic analysis,⁷⁴ based on research we are conducting, that detects weakened defenses against imminent relapse. Previous ACHESS data analyses found patterns of drinkers' word use in discussion groups (e.g. increase in swear words) that signaled impending relapse (R²=.40). For ACHESS-C and FamCHESS-C, we propose to modify analyses so that they immediately identify such patterns, allowing us to rapidly push tailored interventions. (This analysis currently occurs offline.)

FamCHESS-C services. The following ABCT services, from PartnerCHESS, will be available in the FamCHESS-C app but not in ACHESS-C:

ABCT tutorials. Interactive e-learning modules explaining key ABCT skills, including: partner helping drinker with triggers and cravings, supporting change, self-care, partner-assisted relapse prevention, enhancing pleasant activities together, and improving communication. Figure 2 shows a sample tutorial screen.

Agreements between drinker and partner to follow key principles.

Trigger identification and removal. During set-up, the drinker and partner enter triggers. FamCHESS-C prompts dyads to identify coming trigger events and reminds them of ways to address each.

Cravings discussion. Ecological momentary assessments track preconditions for relapse, review urge reduction options, and encourage partner discussions on causes and managing urges.

*Relapse plan.* Monitoring and reminders of steps that have been planned for relapse prevention.

Reminders. Reminders to notice something positive in one's partner, of reasons to stay sober, to take meds, etc.

Structure of FamCHESS-C system. FamCHESS-C will have two complementary versions—one for the drinker, one for the family partner—that in some services will contain different, role-relevant information. For instance, the Instant Library for the partner contains partner-related stories and other material on self-care during crisis. That content does not appear in the drinker version. Additionally, some permissions within services differ by role. For example, partners can communicate with other partners in the discussion group, and patients with other patients, but partners cannot read patients' discussion group posts and vice versa. This enables users to engage in a peer network for more candid interactions.

Drinkers and their family partners can access FamCHESS-C when and how they wish, but the system will also push notifications to them. Thus FamCHESS-C does not rely on user initiative alone to drive engagement. Examples: Drinkers will receive notifications when it is time to take a survey or when they are near a high-risk location. Partners will receive notice of a new post in the partner discussion group, prompts to notice a nice thing, and alerts if the drinker has pushed the crisis button. In the real world, access to FamCHESS-C could be indefinite for ongoing maintenance of recovery and relationship functioning.

